6.4.8 Hy's law

Cases where a patient shows elevations in liver biochemistry require further evaluation and occurrences of AST or ALT $\geq 3 \times \text{ULN}$ together with total bilirubin $\geq 2 \times \text{ULN}$ may need to be reported as SAEs. Please refer to Appendix A for further instruction on cases of increases in liver biochemistry and evaluation of Hy's Law

6.4.9 Disease progression

Disease progression can be considered as a worsening of a patient's condition attributable to the disease for which the investigational product is being studied. It may be an increase in the severity of the disease under study and/or increases in the symptoms of the disease. The development of new, or progression of existing metastasis to the primary cancer under study should be considered as disease progression and not an AE. Events, which are unequivocally due to disease progression, should not be reported as an AE during the study.

6.4.10 New Cancers

The development of a new primary cancer should be reported as an AE (see Section 6.4.13 Olaparib Adverse Events of Special Interest) and would in most cases meet seriousness criteria (with the exception of some non-melanoma skin cancers). New primary malignancies are those that are not the primary reason for the administration of the study treatment and have developed after the inclusion of the patient into the study. They do not include metastases of the original cancer. Symptoms of metastasis or the metastasis itself should not be reported as an AE/SAE, as they are considered to be disease progression.

Adverse Events (AEs) for malignant tumours reported during a study should generally be assessed as Serious AEs. If no other seriousness criteria apply, the 'Important Medical Event' criterion should be used. In certain situations, however, medical judgement on an individual event basis should be applied to clarify that the malignant tumour event should be assessed and reported as a Non-Serious AE. For example, if the tumour is included as medical history and progression occurs during the study, but the progression does not change treatment and/or prognosis of the malignant tumour, the AE may not fulfill the attributes for being assessed as Serious, although reporting of the progression of the malignant tumor as an AE is valid and should occur. Also, some types of malignant tumours, which do not spread remotely after a routine treatment that does not require hospitalization, may be assessed as Non-Serious; examples include Stage 1 basal cell carcinoma and Stage 1A1 cervical cancer removed via cone biopsy.

The above instruction applies only when the malignant tumour event in question is a new malignant tumour (i.e., it is not the tumour for which entry into the study is a criterion and that is being treated by the IP under study and is not the development of new or progression of existing metastasis to the tumour under study). Malignant tumours that – as part of normal, if rare, progression – undergo transformation (e.g., Richter's transformation of B cell chronic lymphocytic leukemia into diffuse large B cell lymphoma) should not be considered a new malignant tumour.

6.4.11 Lack of efficacy

When there is deterioration in the cancer, for which the study treatment(s) is being used, there may be uncertainty as to whether this is lack of efficacy or an AE. In such cases, unless the Sponsor or the reporting physician considers that the study treatment contributed to the deterioration of the condition, or local regulations state to the contrary, the deterioration should be considered to be a lack of efficacy and not an AE.

6.4.12 Deaths

All deaths that occur during the study, or within the protocol-defined 30-day post-study follow-up period after the administration of the last dose of study treatment, must be reported as follows:

- Death clearly the result of disease progression should be reported to the study monitor at the next monitoring visit and should be documented in the CRF but should not be reported as an SAE.
- Where death is not due (or not clearly due) to progression of the disease under study, the AE causing the death must be reported to the study monitor as a SAE within **24 hours** (see Section 8.4.1 for further details). The report should contain a comment regarding the co-involvement of progression of disease, if appropriate, and should assign main and contributory causes of death. This information can be captured in the CRF.

Deaths with an unknown cause should always be reported as a SAE. A postmortem maybe helpful in the assessment of the cause of death, and if performed a copy of the post-mortem results should be forwarded to AstraZeneca within the usual timeframes.

6.4.13 Olaparib adverse events of special interest

Adverse events of special interest [AESI] are events of scientific and medical interest specific to the further understanding of olaparib's safety profile and require close monitoring and rapid communication by the investigators to AstraZeneca. Adverse Events of Special Interest for olaparib are the Important Identified Risks of MDS/AML, and the Important Potential Risks of new primary malignancy (other than MDS/AML) and pneumonitis.

A questionnaire will be sent to any investigator reporting an AESI, as an aid to provide further detailed information on the event. During the study there may be other events identified as AESIs that require the use of a questionnaire to help characterise the event and gain a better understanding regarding the relationship between the event and study treatment.

6.5 Safety reporting and medical management

6.5.1 Reporting of serious adverse events

All SAEs have to be reported, whether or not considered causally related to the investigational product, or to the study procedure(s). All SAEs will be recorded in the CRF.

If any SAE occurs in the course of the study, then Investigators or other site personnel inform the appropriate AstraZeneca representatives within one day i.e., immediately but **no later than 24 hours** of when he or she becomes aware of it.

The designated AstraZeneca representative works with the Investigator to ensure that all the necessary information is provided to the AstraZeneca Patient Safety data entry site **within 1 calendar day** of initial receipt for fatal and life-threatening events **and within 5 calendar days** of initial receipt for all other SAEs.

For fatal or life-threatening adverse events where important or relevant information is missing, active follow-up is undertaken immediately. Investigators or other site personnel inform AstraZeneca representatives of any follow-up information on a previously reported SAE within one calendar day i.e., immediately but **no later than 24 hours** of when he or she becomes aware of it.

For further guidance on the definition of a SAE, see Appendix B of the Clinical Study Protocol.

6.5.2 Pregnancy/Paternal exposure

Male patients should refrain from fathering a child or donating sperm during the study and for 3 months following the last dose.

Pregnancy of the patient's partners is not considered to be an adverse event. However, the outcome of all pregnancies (spontaneous miscarriage, elective termination, ectopic pregnancy, normal birth or congenital abnormality) occurring from the date of the first dose until 3 months *after the last dose* should, if possible, be followed up and documented.

6.5.3 Overdose

There is currently no specific treatment in the event of overdose with olaparib and possible symptoms of overdose are not established.

Olaparib must only be used in accordance with the dosing recommendations in this protocol. Any dose or frequency of dosing that exceeds the dosing regimen specified in this protocol should be reported as an overdose. The Maximum Tolerated Dose is 300 mg twice daily (tablet).

Adverse reactions associated with overdose should be treated symptomatically and should be managed appropriately.

- An overdose with associated AEs is recorded as the AE diagnosis/symptoms on the relevant AE modules in the CRF.

For overdoses associated with a SAE, the standard reporting timelines apply, see Section 6.4.2. For other overdoses, reporting must occur within 30 days.

6.5.4 Medication error

If a medication error occurs in the course of the study, then the Investigator or other site personnel informs the appropriate AstraZeneca representatives within 1 day i.e., immediately but no later than 24 hours of when he or she becomes aware of it.

The designated AstraZeneca representative works with the Investigator to ensure that all relevant information is completed within 1 (Initial Fatal/Life-Threatening or follow up Fatal/Life-Threatening) or 5 (other serious initial and follow up) calendar days if there is an SAE associated with the medication error (see Section 6.4.2) and within 30 days for all other medication errors.

The definition of a Medication Error can be found in Appendix B.

6.5.5 Management of adverse events

Any toxicity observed during the course of the study could be managed by interruption of the dose of study treatment or dose reductions. Repeat dose interruptions are allowed as required, for a maximum of 4 weeks on each occasion. Study treatment can be dose reduced to 250 mg twice daily as a first step and to 200 mg twice daily as a second step. If the reduced dose of 200 mg twice daily is not tolerable, no further dose reduction is allowed, and study treatment should be discontinued.

Once dose is reduced, escalation is not permitted (except following concomitant treatment with CYP3A4 inhibitors – see Section 6.5

6.5.5.1 Management of hematological toxicity

Management of anemia

Table 10 Management of anemia

Hemoglobin	Action to be taken
Hb < 10 but \geq 8 g/dl (CTCAE Grade 2)	First occurrence: Give appropriate supportive treatment and investigate causality. Investigator judgement to continue olaparib with supportive treatment (eg transfusion) or interrupt dose for a maximum of 4 weeks. Study treatment can be restarted if Hb has recovered to > 9 g/dl. Subsequent occurrences: If Hb < 10 but \geq 9 g/dl investigator judgement to continue olaparib with supportive treatment (eg. transfusion) or dose interrupt (for max of 4 weeks) and upon recovery dose reduction may be considered (to 250 mg twice daily as a first step and to 200 mg twice daily as a second step). If Hb < 9 but \geq 8 g/dl, dose interrupt (for max of 4 weeks) until Hb \geq 9 g/dl and upon recovery dose reduction may be considered (to 250 mg twice daily as a first step and to 200 mg twice daily as a second step).

Hemoglobin	Action to be taken
Hb < 8 g/dl (CTCAE Grade 3)	Give appropriate supportive treatment (e.g. transfusion) and investigate causality. Interrupt olaparib for a maximum of 4 weeks until improved to Hb \geq 9 g/dl. Upon recovery dose reduce to 250 mg twice daily as a first step and to 200 mg twice daily as a second step in the case of repeat Hb decrease.

Common treatable causes of anemia (e.g., iron, vitamin B12 or folate deficiencies and hypothyroidism) should be investigated and appropriately managed. In some cases, management of anemia may require blood transfusions. For cases where patients develop prolonged hematological toxicity (\geq 2 week interruption/delay in study treatment due to CTC grade 3 or worse anemia and/or development of blood transfusion dependence), refer to guidance later in this section for the management of this.

Management of neutropenia, leukopenia and thrombocytopenia

Table 11 Management of neutropenia, leukopenia and thrombocytopenia

Toxicity	Study treatment dose adjustment
CTCAE Grade 1-2	Investigator judgement to continue treatment or if dose interruption, this should be for a maximum of 4 weeks; appropriate supportive treatment and causality investigation
CTCAE Grade 3-4	Dose interruption until recovered to CTCAE gr 1 or better for a maximum of 4 weeks. If repeat CTCAE grade 3-4 occurrence, dose reduce olaparib to 250 mg twice daily as a first step and 200 mg twice daily as a second step

Adverse event of neutropenia and leukopenia should be managed as deemed appropriate by the investigator with close follow up and interruption of study drug if CTC grade 3 or worse neutropenia occurs.

Primary prophylaxis with Granulocyte colony-stimulating factor (G-CSF) is not recommended, however, if a patient develops febrile neutropenia, study treatment should be stopped and appropriate management including G-CSF should be given according to local hospital guidelines. Please note that G-CSF should not be used within at least 24 h (7 days for pegylated G-CSF) of the last dose of study treatment unless absolutely necessary.

Platelet transfusions, if indicated, should be done according to local hospital guidelines.

For cases where patients develop prolonged haematological toxicity (\geq 2 week interruption/delay in study treatment due to CTC grade 3 or worse), refer to guidance later in this section for the management of this.

Management of prolonged hematological toxicities while on study treatment

If a patient develops prolonged hematological toxicity such as:

- ≥ 2 week interruption/delay in study treatment due to CTC grade 3 or worse anaemia and/or development of blood transfusion dependence
- ≥ 2 week interruption/delay in study treatment due to CTC grade 3 or worse neutropenia ($\text{ANC} < 1 \times 10^9/\text{L}$)
- ≥ 2 week interruption/delay in study treatment due to CTC grade 3 or worse thrombocytopenia and/or development of platelet transfusion dependence (Platelets $< 50 \times 10^9/\text{L}$)

Check weekly differential blood counts including reticulocytes and peripheral blood smear. If any blood parameters remain clinically abnormal after 4 weeks of dose interruption, the patient should be referred to hematologist for further investigations. Bone marrow analysis and/or blood cytogenetic analysis should be considered at this stage according to standard hematological practice. Study treatment should be discontinued if blood counts do not recover to CTC gr 1 or better within 4 weeks of dose interruption.

Development of a confirmed myelodysplastic syndrome or other clonal blood disorder should be reported as an SAE and full reports must be provided by the investigator to AstraZeneca Patient Safety. Olaparib treatment should be discontinued if patient's diagnosis of MDS and/or AML is confirmed.

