5.1 Inclusion criteria

Patients are eligible to be included in the study only if all of the following inclusion criteria and none of the exclusion criteria apply:

1. Capable of giving signed informed consent which includes compliance with the requirements and restrictions listed in the informed consent form (ICF) and in this protocol.
2. Subject must be \geq 18 years of age at the time of signing the informed consent form.
3. Individuals who have documented histologically confirmed adenocarcinoma of the prostate.
4. Subject must have evidence of castration resistant prostate cancer as evidenced by PSA progression (per Prostate Cancer Working Group 3 [PCWG3] criteria) and a castrate serum testosterone level (i.e. \leq 50 mg/dL)¹.
5. PSA must be at least 2 ng/mL and rising on two successive measurements at least two weeks apart.
6. At least one lesion (measurable and/or non-measurable) that can be accurately assessed at baseline by CT scan, MRI, or PET and is suitable for repeated assessment.
7. Must have progressed on abiraterone and/or a second-generation AR antagonist (i.e. enzalutamide, apalutamide, or darolutamide). If these were given in the hormone sensitive setting, patients must also have progressed on at least one prior approved therapy for CRPC.
8. Must have archival tissue available or be willing to undergo metastatic biopsy in order to perform next-generation DNA sequencing and undergo whole exome sequencing.
9. Patient must have a positive LOH score on prior UW OncoPlex testing

10. Patients must have normal organ and bone marrow function measured within 28 days prior to administration of study treatment as defined below:

- Hemoglobin ≥ 10.0 g/dL with no blood transfusion in the past 28 days
- Absolute neutrophil count (ANC) $\geq 1.5 \times 10^9$ /L
- Platelet count $\geq 100 \times 10^9$ /L
- Total bilirubin $\leq 1.5 \times$ institutional upper limit of normal (ULN)
- Aspartate aminotransferase (AST) (Serum Glutamic Oxaloacetic Transaminase (SGOT)) / Alanine aminotransferase (ALT) (Serum Glutamic Pyruvate Transaminase (SGPT)) $\leq 2.5 \times$ institutional upper limit of normal unless liver metastases are present in which case they must be ≤ 5 x ULN
- Patients must have creatinine clearance estimated of ≥ 51 mL/min using the Cockcroft-Gault equation or based on a 24 hour urine test:

$$\text{Estimated creatinine clearance} = \frac{(140 - \text{age [years]}) \times \text{weight (kg)}}{\text{serum creatinine (mg/dL)} \times 72}$$

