6.3.1.2 Bone marrow or blood cytogenetic samples

Bone marrow or blood cytogenetic samples may be collected for patients with prolonged hematological toxicities as defined in Section 6.5.5.1

Bone marrow analysis should include an aspirate for cellular morphology, cytogenetic analysis and flow cytometry, and a core biopsy for bone marrow cellularity. If it is not possible to conduct cytogenetic analysis or flow cytometry on the bone marrow aspirate, then attempts should be made to carry out the tests on a blood sample. Full reports must be provided by the investigator for documentation on the Patient Safety database. These data are not required to be entered into CRF.

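### Section 6.5.5.1 names transfusion dependence as prolonged hematological toxicity, but its referral, marrow and non-recovery stopping steps run from a 4-week hold that Table 10 need not produce

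*Combined protocol and SAP*

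**What the plan says.** All places are in the combined protocol and SAP.

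- **Trigger (6.5.5.1, prolonged toxicities).** The anemia example is a 2-week or longer "interruption/delay in study treatment due to CTC grade 3 or worse anaemia and/or development of blood transfusion dependence". The text under Table 10 describes the same situation and sends the reader to this guidance.
- **Actions (same text).** One action carries no time condition: "Check weekly differential blood counts including reticulocytes and peripheral blood smear". Referral does carry one: "If any blood parameters remain clinically abnormal after 4 weeks of dose interruption, the patient should be referred to hematologist for further investigations". The next sentence depends on that point: "Bone marrow analysis and/or blood cytogenetic analysis should be considered at this stage according to standard hematological practice". Treatment is then to be discontinued if counts have not returned to grade 1 or better within 4 weeks of interruption.
- **Table 10 (6.5.5.1).** For a first Hb of 8 to <10 g/dl: "Investigator judgement to continue olaparib with supportive treatment (eg transfusion) or interrupt dose for a maximum of 4 weeks". The same choice is given for later values of 9 to <10. A hold is required for later values of 8 to <9 and for any value below 8, and it ends when Hb is at least 9.
- **6.5.5.** "Repeat dose interruptions are allowed as required, for a maximum of 4 weeks on each occasion".
- **6.3.1.2.** "Bone marrow or blood cytogenetic samples may be collected for patients with prolonged hematological toxicities as defined in Section 6.5.5.1".
- **Entry (5.1, criterion 10).** Hb must be at least 10.0 g/dl "with no blood transfusion in the past 28 days". No similar statement about transfused values accompanies the on-treatment restart thresholds.

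**The concern.** Transfusion dependence can develop while the drug is still being taken, because Table 10 allows exactly that. The steps that would lead from it to a hematologist, to a marrow or cytogenetic work-up, or to stopping for non-recovery all presuppose a 4-week hold. One of the pathway's named triggers is therefore not connected to its main consequences.

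This matters because MDS/AML is the only Important Identified Risk among the olaparib events of special interest in section 6.4.13. Stopping olaparib for confirmed MDS/AML is untimed, but it needs a diagnosis first, and the referral and marrow steps are the ones that could lead to it. At stake are participant safety and uniform handling by investigators. The primary PSA analysis is not affected.

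**Working it through.** The plan states no figure on this point, so the check sets the rules side by side.

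**1. How much hold does Table 10 require?**

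| Hb (g/dl) | Hold required? | Hold ends at | Can it stay under 4 weeks? |
|---|---|---|---|
| 8 to <10, first occurrence | No, investigator judgment | above 9, if held | Yes, can be 0 weeks |
| 9 to <10, later | No, investigator judgment | recovery, level not given | Yes, can be 0 weeks |
| 8 to <9, later | Yes, 4 weeks at most | at least 9 | Yes, if Hb reaches 9 sooner |
| below 8 | Yes, 4 weeks at most | at least 9 | Yes, if Hb reaches 9 sooner |

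Transfusion is one of the supportive treatments the table names, and nothing says whether Hb measured after a transfusion counts toward 9.

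**2. Do holds add up?** Section 6.5.5 sets the limit per occasion, and 6.5.5.1 does not say that its 4 weeks are cumulative. As an illustration, two holds of 2 weeks total 2 + 2 = 4 weeks off drug, but neither is a 4-week hold.

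**3. How many rounds are possible?** In the 8 to <10 band a dose reduction is at most something to consider, and no number of rounds is set. Below 8 g/dl the dose must come down after each recovery (300, then 250, then 200 mg twice daily). Up to three dose levels can therefore each see a hold shorter than 4 weeks before no further reduction is allowed.

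**4. Two readings of the trigger.** The documents do not define transfusion dependence, and the 'and/or' can attach in two ways.

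- *Stand-alone trigger.* The man enters the pathway and has weekly counts, but no stated point at which referral is due unless a hold lasts 4 weeks.
- *A cause of the 2-week interruption.* A man transfused while dosing continues does not enter the pathway at all.

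**5. Two readings of the stopping clock.** The 4 weeks for non-recovery could mean 4 weeks spent on hold, or 4 weeks counted from the start of a hold. On the second reading, a man who restarted early at Hb 9 could still meet the stopping rule. A man who was never held has no clock on either reading.

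**6. Recovery criterion.** Table 10 labels Hb 8 to <10 as grade 2, so a value from 9 to <10 is still grade 2 by the protocol's own label. Take a man held for at least 2 weeks for Hb below 8 whose Hb is between 9 and 10 at week 4. Table 10 restarts him at a reduced dose. Section 6.5.5.1 discontinues him because he is not at grade 1. Both cannot apply. Table 11, for grade 3-4 neutropenia, leukopenia and thrombocytopenia, does use recovery to grade 1 or better, so this conflict is confined to anemia.

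**7. Marrow sampling.** Section 6.3.1.2 permits samples from anyone who meets the 6.5.5.1 definition, with no 4-week condition. Section 6.5.5.1 asks that sampling be considered at the 4-week point. The conditions differ, and neither makes sampling mandatory.

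**The case against.** The strongest reply is that the protocol does not leave such a man unattended.

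- Table 10 calls for the cause to be investigated at a first grade 2 value and at Hb below 8, and the text below it asks for treatable causes to be investigated.
- The weekly checks include reticulocytes and a blood smear.
- Section 6.3.1.2 allows marrow or cytogenetic sampling without waiting 4 weeks.
- Appendix B 5 gives anemia requiring transfusion as an example of an important medical event, and section 6.5.1 requires SAEs to be reported within 24 hours. Repeated transfusion would usually produce repeated reports.
- Section 6.4 sets weekly safety meetings, 6.4.3 requires events to be followed, and 6.4.2.1 prompts for MDS/AML during survival follow-up.
- A man whose Hb stays below 9 despite transfusion, where a hold is required, does reach the 4-week point. Section 5.11 lets the investigator discontinue treatment for an adverse event, and 6.5.5 requires stopping if 200 mg twice daily is not tolerable.

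All of this stands, and it reduces the consequence. None of it sets a referral point for transfusion dependence or resolves the grade 1 conflict.

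A reader might infer more than the text supports:

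- *That referral is never reached, or that every later action waits for 4 weeks.* The correct statement is that the three steps named need not be reached. Sampling under 6.3.1.2 and the actions on confirmed MDS/AML are not tied to 4 weeks.
- *That MDS/AML cases will go unrecognized, or that events of special interest will be undercounted.* Section 6.9.2 plans no separate count of such events, and the follow-up prompts would pick up later diagnoses.
- *That the entry criterion contradicts Table 10.* A baseline eligibility condition serves a different purpose from a restart threshold. It shows only that transfused values were considered at entry and not addressed on treatment.

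**Conclusion.** The concern holds as a mismatch between the protocol's own rules. A transfusion-dependent man need not reach referral, consideration of marrow or cytogenetic analysis, or the non-recovery stop; on one reading of the trigger he may not enter the pathway. Separately, Table 10 and the prolonged-toxicity text give opposite instructions for a man held for grade 3 anemia whose Hb recovers only to between 9 and 10 g/dl.

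The size cannot be calculated, because the documents give no rate of transfusion or of MDS/AML. With 30 men planned, few are likely to be affected. The first conclusion assumes that the 4 weeks are not cumulative and that a post-transfusion Hb can end a hold; the text settles neither. For a man dosed throughout with no hold, it needs neither assumption. The grade conflict rests only on Table 10's own labels. The point deserves correction because it bears on participant safety and the remedy is wording.

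**What to change.** Reconcile Table 10, the prolonged-toxicity text in 6.5.5.1 and section 6.3.1.2 so that they agree on:

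- what triggers the pathway, with the 'and/or' made unambiguous and transfusion dependence defined;
- the time reference for referral, marrow or cytogenetic analysis, and stopping, including whether holds are counted singly or together;
- the recovery criterion for anemia;
- whether a post-transfusion Hb counts as recovery.

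The sponsor's medical lead should set each rule; none is proposed here. The cost is a protocol wording change in one table, one block of text and one short section, with possibly some earlier hematology referrals. Sample size and planned analyses do not change.

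### After a prolonged hold for grade 3 anaemia, a haemoglobin of 9.0 to below 10 g/dl at week 4 meets Table 10's restart level but fails the prolonged-toxicity rule's grade 1 requirement

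*Combined protocol and SAP*

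**What the plan says.** Three parts of Section 6.5.5.1 bear on anaemia.

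- **Table 10, grades.** Hb below 10 and at least 8 g/dl is labelled CTCAE grade 2. Hb below 8 g/dl is labelled grade 3.
- **Table 10, restart levels.** In the grade 3 row the instruction is "Interrupt olaparib for a maximum of 4 weeks until improved to Hb" of at least 9 g/dl, followed by a dose reduction on recovery. In the grade 2 row, a first occurrence carries the rule "Study treatment can be restarted if Hb has recovered to > 9 g/dl". A later occurrence with Hb from 8 to below 9 uses at least 9.
- **Prolonged hematological toxicity.** The anaemia trigger is a hold of 2 weeks or more, worded as a "week interruption/delay in study treatment due to CTC grade 3 or worse anaemia and/or development of blood transfusion dependence". The consequence is "Study treatment should be discontinued if blood counts do not recover to CTC gr 1 or better within 4 weeks of dose interruption". No exception is made for haemoglobin.

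The paragraph under Table 10 sends men who meet this trigger to the prolonged-toxicity text, so the two rules are meant to apply to the same patients. Table 11, for neutropenia, leukopenia and thrombocytopenia, makes grade 1 or better the recovery level, which agrees with the prolonged-toxicity text.

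**The concern.** The protocol uses two recovery levels for the same hold. Table 10's restart level for a grade 3 hold lies inside the band that the table itself calls grade 2, while the prolonged-toxicity text accepts only grade 1 or better. Where both apply, one tells the investigator to resume and the other to stop.

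What is at stake is a stop-or-continue instruction for a toxicity that Section 2.2 lists among the known risks of olaparib. Two investigators who each follow the protocol could do opposite things, and either action could be recorded as a deviation. Section 5.1 admits men from Hb 10.0 g/dl, the upper edge of the grade 2 band. The same decision settles whether a man is still on treatment when the PSA values that define the primary endpoint begin, at Cycle 4.

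**Working it through.** No sample size or power figure enters the point itself. The check compares thresholds, using only the protocol's own grade labels.

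**Inputs (Section 6.5.5.1)**
- Grade 2 band, G2: 8 ≤ Hb < 10.
- Restart region after a grade 3 hold, R: Hb ≥ 9, within 4 weeks.
- Prolonged-toxicity requirement: grade 1 or better within 4 weeks, so any value in G2 fails it.
- Population: held at least 2 weeks for grade 3 or worse anaemia, or transfusion dependent.

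**Overlap**
R ∩ G2 = {Hb ≥ 9} ∩ {8 ≤ Hb < 10} = {9 ≤ Hb < 10}.

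**A man held at least 2 weeks for Hb below 8, by his Hb at week 4**

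| Hb at week 4 | Table 10, grade 3 row | Prolonged-toxicity text | Result |
|---|---|---|---|
| Below 9 | Restart level not met | Discontinue | No conflict |
| 9.0 to below 10 | Resume at reduced dose | Discontinue (still grade 2) | Opposite instructions |
| 10 or above | Resume at reduced dose | Table 10's grade 2 label no longer applies | This conflict does not arise |

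**Timing**
- Hb reaches 9 in under 2 weeks, without transfusion dependence: the prolonged-toxicity text is not triggered and Table 10 stands alone.
- Hb reaches 9.0 to below 10 after 2 weeks but before week 4: Table 10 allows a restart. The prolonged-toxicity text does not say whether that restart ends its test or whether grade 1 must still be reached by week 4. This is an ambiguity, not a plain contradiction.
- Hb is in the band when week 4 arrives and dosing is still on hold: both rules apply at once and disagree.

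**Does another section settle it?** Section 5.11 lists a hold of more than 4 weeks for an adverse event as a reason treatment may be discontinued. It sets no recovery level, so it does not choose between the two rules. Section 6.5.5 caps each interruption at 4 weeks and is also silent on the level.

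**Inequality within Table 10**
The first-occurrence grade 2 entry requires Hb above 9; the other entries that state a restart level require at least 9. They differ only at exactly 9.0 g/dl.

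**The case against.** The best defence is sequence. Table 10 ends the hold as soon as Hb reaches 9, so a man at 9.3 in week 3 is already back on treatment and has not failed a 4-week limit. Section 5.11 fits this reading, since it speaks of drug still being held after 4 weeks. The argument has force for men who recover before week 4, and for them the text is unclear rather than contradictory. It does not help the man who is in the band when week 4 arrives. Nor does the protocol state this reading anywhere, while it does send these same men to the prolonged-toxicity text.

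It is also fair to say that the difference in inequality is trivial. It matters at a single value, and the stricter entry sits where the investigator may continue olaparib without any hold.

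A reader might infer two stronger things that the documents do not support.

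- **That a man stopped before Cycle 4 is automatically a PSA50 non-responder.** Section 6.9.1 assigns non-response to a man who drops out of the study. Sections 5.11 and 5.11.1 separate stopping treatment from leaving the study and continue data collection. The Synopsis adds a further subject for a dropout, and Section 6.9.1 bases the primary analysis on men with 12 weeks of follow-up if dropout exceeds expectation. How a man stopped early is counted is a separate open question.
- **That one such man could turn the trial's result.** One response in 20 is 1/20 = 5 percentage points, and the exact binomial tail against 20% is 0.032 for 8/20 and 0.087 for 7/20. Although 0.032 is close to the one-sided 0.03 used for sizing in Section 6.8, Section 6.9.1 names no exact test. It plans a 90% Wilson interval: 24.2% to 58.1% for 8/20 and 20.2% to 53.3% for 7/20. Both lower limits exceed 20%, so this change of one patient does not cross the null rate under the planned interval.

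**Conclusion.** The contradiction is real and rests on the protocol's own grade labels. It is confined to men held at least 2 weeks for grade 3 or worse anaemia, or transfusion dependent, whose Hb is 9.0 to below 10 g/dl at week 4. Hb of 10 or above creates no conflict, and below 9 the rules do not disagree. Men in this group who reach the band before week 4 meet an ambiguity that the text should close.

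The number of men affected cannot be estimated: the documents give no rate of grade 3 anaemia, of holds of 2 weeks or more, or of partial recovery. An effect on the PSA50 rate is possible. It would require an iHRD-positive man who would otherwise have responded and whose treatment was stopped early enough to affect his PSA from Cycle 4 onward. It cannot be sized, and the point does not depend on it. The case for acting is that a patient-safety rule gives two opposite answers.

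Nothing here implies a view on which recovery level is right.

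**What to change.** The sponsor should reconcile Table 10 with the prolonged-toxicity text in Section 6.5.5.1:

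1. Apply one recovery criterion and one consequence at 4 weeks to anaemia after a prolonged hold.
2. State whether a restart under Table 10 ends the prolonged-toxicity test or leaves it running to week 4.
3. Use the same inequality for the restart level throughout Table 10.

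The choice of level and consequence is for the sponsor's clinical team. The cost is amendment wording; sample size, visit schedule and planned analyses need not change.
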